7.1.1. Intensity Assessment

The investigator or the designated person will provide an assessment of the severity of each AE by recording a severity rating on the appropriate AE reporting page of the subject's eCRF. In classification of AEs, the term "severe" is not the same as "serious". Severity is a description of the intensity of a specific event (as in mild, moderate, or severe chest pain). The term "serious" relates to a participant/event outcome or action criteria, usually associated with events that pose an immediate threat to a participant's life or functioning, and meet one or more of the SAE criteria described above.

The DAIDS Table for Grading the Severity of Adult and Pediatric Adverse Events, Version 2.1 will be used for assessing AEs (DAIDS Table for Grading the Severity of Adult and Pediatric Adverse Events, Version 2.1. [July 2017]). All AEs will be graded as grade 1 (mild), grade 2 (moderate), grade 3 (severe), grade 4 (potentially life-threatening), or grade 5 (death) according to the definitions described in the DAIDS Table. Every effort will be made to obtain an adequate evaluation of the severity.

7.1.2. Causality Assessment

The qualified investigator or a medically qualified designate will determine the relationship of any AE to study drugs using the following guidelines in Table 2.

Table 2: Adverse Event Relationship to Study Drug

Relationship to Drug	Comment
Reasonable Possibility	There is evidence to suggest a causal relationship between the drug(s) and the AE (eg, AE is uncommon and known to be strongly associated with drug exposure or is uncommon in the study population, but not commonly associated with drug exposure).
No Reasonable Possibility	There is no evidence to suggest a causal relationship between the drug(s) and the AE.

7.2. Routine Reporting

For the purposes of this study, non-serious AEs and SAEs will be recorded in the eCRF from the time of informed consent through Day 29 (the primary study period). SAEs will be recorded through Day 60.

During these periods, all AEs spontaneously reported by the subject, observed by the clinical staff, or elicited by general questioning will be recorded and reported in the eCRF.

Any AE which remains unresolved as of the last visit will require follow-up until the AE has been resolved, a reasonable explanation for its persistence found, or is deemed chronic or stable by the investigator. It is the investigator's responsibility to ensure subjects experiencing AEs receive appropriate follow-up, treatment where required, and that every action is well documented.

Classification will be performed by System Organ Class (SOC) and preferred term using the Medical Dictionary for Regulatory Activities (MedDRA).

In general, AEs occurring secondary to other events (eg, clinical sequelae or a cascade of events) should be identified by their primary cause. For example, if severe vomiting is known to result in dehydration, it is sufficient to record only vomiting as an SAE or AE in the eCRF. However, medically significant AEs occurring secondary to an initiating event that are separated in time should be recorded as independent events on the eCRF.

7.3. Serious Adverse Event Reporting

Clinical sites must notify of any SAE, without regard to causality, within 24 hours after becoming aware of its occurrence. Any non-serious AE which worsens and eventually meets the criteria for an SAE must also be reported as a new SAE.

Information regarding SAEs will be transmitted to celevate using the Serious Adverse Event form in the electronic data collection tool, which must be completed by a member of the investigational site staff within 24 hours. This form should include a clearly written narrative describing diagnostic terms, signs, symptoms, and treatment of the event; diagnostic procedures; as well as any relevant laboratory data and an assessment of the potential causal relationship between the event and the investigational product(s). Information not available at the time of the initial report (eg an end date for the AE, laboratory values received after the report, or hospital discharge summary) must be documented. All follow-up information must be reported as soon as the relevant information is available.

If the electronic system is unavailable, then the site will use the paper SAE data collection tool and transmit to collection within 24 hours by one of the following methods:

Email: PPD	
Fax:PPD	

The site will enter the SAE data into the electronic system as soon as it becomes available.

Contact information for the Sponsor's physician is also listed below, should the sites need to contact the Sponsor to discuss any medical, safety related questions, or SAEs:

PPD Atea Pharmaceuticals, Inc.
Telephone PPD
Email: PPD

An unlisted (unexpected) SAE is one in which the nature or severity is not consistent with the applicable product reference safety information (RSI). For investigational product(s), the expectedness of an SAE will be determined by whether or not it is listed in the RSI within the Investigator's Brochure(s). Investigators will be notified, and the Investigator's Brochure will be updated, if any new pattern of AEs or laboratory abnormalities is found to be related to BEM dosing.

The start date of an SAE reported on the Serious Adverse Event form must be the same as the start date of the corresponding AE documented on the eCRF. If a change in severity is noted for the existing AE, it must be recorded. If a worsened AE meets the criteria for an SAE, the start date of the SAE must be the same as the start date of the worsened AE.

All SAEs that have not resolved by the end of the study, or that have not resolved upon discontinuation of the subject's participation in the study, must be followed until any of the following occurs:

- The event resolves
- The event stabilizes
- The event returns to baseline, if a baseline value is available
- The event can be attributed to agents other than the study drugs or to factors unrelated to study conduct
- It becomes unlikely that any additional information can be obtained (subject or health care practitioner refusal to provide additional information, lost to follow-up after demonstration of due diligence with follow-up efforts)

Any SAE reports will be reported by the investigators (or designee) to their local IRB/IEC in accordance with local reporting requirements and reporting timelines.

Similarly, the Sponsor (or designee) will determine whether an SAE must be reported in an expedited manner to regulatory authorities, in accordance with regulatory requirements, including auxiliary medicinal products to Eudravigilance per Directive 2001/83/EC where appropriate. If so, the Sponsor (or designee) will report the event to the regulatory authorities in accord with applicable reporting timelines.

7.4. Pregnancy Reporting

All initial reports of pregnancy in female subjects during the study (until 30 days after the last dose of study drug) or female partners of male subjects, where locally required, must be reported to cell (see Section 7.3 for contact information) by the investigational staff within 24 hours of their knowledge of the event by completing the "Pregnancy Notification" section of the designated form. All pregnancies will be followed-up to determine the outcome including

spontaneous or voluntary termination, details of birth, presence or absence of any birth defects, congenital anomalies, maternal and/or newborn complications, or longer where locally required. After the expected pregnancy end date, the site will complete the "Pregnancy Outcome" section of the designated form and provide to the CCI. Abnormal pregnancy outcomes are considered SAEs and must be reported using the electronic Serious Adverse Event form. Any subject who becomes pregnant during treatment must immediately discontinue study drug.

8. STATISTICAL ANALYSES

This section summarizes the statistical analyses pertinent to the assessments in this study. A statistical analysis plan (SAP) describing the detailed statistical methods will be developed and finalized before any analyses are performed.

8.1. Analysis Populations

8.1.1. Safety Population

The safety population will include all subjects who received at least one dose of the study drug (BEM or placebo). The study population will be analyzed as treated.

8.1.2. Intention to Treat Population

The intention to treat (ITT) population will include all randomized subjects and will be analyzed as randomized.

8.1.3. Modified Intent-to-Treat Population

The modified intent-to-treat (mITT) population includes all randomized subjects who received ≥1 dose of study drug and have ≥ 1 positive SARS-CoV-2 result (from NP swab samples via central testing) through Day 5. The majority of subjects are expected to have the positive SARS-CoV-2 qualifying sample at baseline, but the window is extended to allow the inclusion of subjects who may have a baseline false negative or missing sample at baseline.

The modified intent-to-treat-S (mITT-S) population includes all randomized subjects who received ≥ 1 dose of study drug, have ≥ 1 positive SARS-CoV-2 result (from NP swab samples via central testing) through Day 5, and who are stratified into the supportive-care-only population.

The modified intent-to-treat-C (mITT-C) population will include all randomized subjects who received ≥ 1 dose of study drug, have ≥ 1 positive SARS-CoV-2 result (from NP swab samples via central testing) through Day 5, and who are stratified into the combination antiviral population.

For analyses and displays based on mITT-S and mITT-C analysis sets, subjects will be classified according to randomized treatment.

8.1.4. PK Population

The PK population will include all subjects who received at least one dose of BEM and for whom evaluable plasma concentration data are available. Subjects who received placebo will not be included in the PK population.

8.2. Endpoints

The primary efficacy endpoint is the proportion of subjects in the supportive-care-only population who are hospitalized for any cause or who died due to any cause through Day 29.

The secondary endpoints are:

Efficacy:

- Proportion of subjects with COVID-19-related hospitalization or who died due to any cause through Day 29
- Proportion of subjects who died due to any cause through Day 29 and Day 60
- Proportion of subjects with COVID-19-related complications (eg., death, hospitalization, radiologically confirmed pneumonia, acute respiratory failure, sepsis, coagulopathy, pericarditis/myocarditis, cardiac failure) through Day 29
- Proportion of subjects with COVID-19-related medically attended visits (hospitalization, emergency room (ER) visit, urgent care visit, physician's office visit, or telemedicine visit) or who died due to any cause through Day 29 and Day 60
- Proportion of subjects with COVID-19 symptom relapse (term to be defined in the SAP) through Day 29
- Proportion of subjects with viral load rebound (term to be defined in the SAP) through Day 29

Safety:

• The incidence and severity of adverse events (AEs) and serious adverse events (SAEs)

The exploratory endpoints are:

Efficacy:

- Time to alleviation or improvement of individual COVID-19 symptoms
- Time to self-reported return to usual (pre-COVID-19) health
- Proportion of subjects requiring post-randomization rescue therapy

Note: For subjects randomized into the combination antiviral population, antiviral medications administered post-baseline within 24 hours of first study drug, as part of the combination regimen, are not considered rescue medication.

Note: Rescue therapy for the purpose of the endpoint includes only treatments with direct activity against SARS-CoV-2; and that is administered for COVID-19-related clinical decline.

- Duration and severity of COVID-19 symptom relapse
- Proportion of subjects with both COVID-19 symptom relapse and viral rebound
- Change from baseline in amount of SARS-CoV-2 viral RNA as measured by RTqPCR over time
- Time to cessation of SARS-CoV-2 viral shedding by RT-qPCR

- Proportion of subjects negative for SARS-CoV-2 viral RNA by RT-qPCR over time
- Area under the curve (AUC) in the amount of SARS-CoV-2 viral RNA as measured by RT-qPCR
- Proportion of subjects with treatment-emergent mutations in SARS-CoV-2 viral genes

•	CCI	

Pharmacokinetics:

 Plasma concentrations of AT-511 (free base form of AT-527 [BEM]) and its metabolites

The primary efficacy endpoint will also be assessed in the combination antiviral population as a secondary endpoint. All secondary celegated endpoints will be assessed in both the supportive-care-only population, and the combination antiviral population.

8.3. Statistical Methods

The primary and secondary efficacy analyses will be conducted using the mITT-S population. Efficacy analyses will be repeated using the mITT-C population.

Safety analyses will be performed on the safety population, which consists of all subjects who received at least one dose of study drug. In all safety analyses, subjects will be grouped according to the treatment that the subjects actually received rather than the treatment assigned at randomization. Here, treatment will be considered as BEM monotherapy and placebo for subjects in the supportive-care-only population and as BEM combination and compatible antiviral in the combination antiviral population.

Demographics and baseline characteristics will be summarized by treatment group and overall for each analysis population. Disposition, with respect to both treatment and study completion, will be summarized by treatment group and overall with reasons for discontinuation tabulated.

For continuous variables, descriptive statistics will include the following information: the number of patients reflected in the calculation (n), mean, standard deviation, Q1, median, Q3, minimum, and maximum. For categorical or ordinal data, frequencies and percentages will be displayed for each category.

Time-to-event endpoints will be analyzed using Kaplan-Meier methods for estimation and log-rank test for treatment comparison.

Data handling for quantitative data that are reported as less than the lower limit of quantification, as well as values reported greater than the upper limit of quantification, will be described in the SAP.

In general, data will be considered as observed, ie, values for missing data will not be imputed.

The primary analysis will occur when all randomized subjects have had sufficient follow-up time to complete the Day 29 visit. Data collected during the extended FU period will be summarized separately, after the primary study analysis.

8.3.1. Primary Efficacy Analysis

The primary efficacy objective of this study is to evaluate the efficacy of BEM based on the proportion of patients who are hospitalized for any cause or who died due to any cause through Day 29 in the supportive-care-only population. The primary estimand is the difference in the proportion of patients who are hospitalized for any cause or who died due to any cause through Day 29 in the supportive-care-only population, and the primary treatment effect comparison will be between the BEM arm and the placebo arm. This proportion will be compared between the BEM and placebo arms using a Cochran-Mantel-Haenszel (CMH) test adjusted for the stratification factors of age and region. The CMH p-value and estimated common risk difference, odds ratio and relative risk, along with the corresponding 95% confidence intervals (CIs) for these estimates, will be presented.

Intercurrent events are those that occur after treatment initiation and either preclude observation of the variable or affect its interpretation. For the intercurrent events of rescue (eg intervention with remdesivir) and concomitant COVID-19 medications, a treatment policy approach will be taken, whereby use of rescue and concomitant medications will be ignored and observations collected after they are administered to the patient will be used. In addition, patients will be followed, assessed, and analyzed irrespective of their completion of the course of the study treatment. The analysis will be performed based on observed data, and the following measures will be used to reduce missing hospitalization/death data: eCRFs capturing clinical information that may be indicative of hospitalization will be reviewed to mitigate the risk of unreported hospitalizations, and study staff may use a public information source to obtain information about survival status if a patient withdraws from the study.

8.3.2. Secondary Efficacy Analyses

Analysis of the primary efficacy endpoint will be conducted for the combination antiviral population as a secondary endpoint. Presentation and analysis of other secondary efficacy endpoints will be carried out using methods similar to those specified for the primary efficacy endpoint. Data handling, analysis populations, and specification of statistical testing for secondary efficacy endpoints, with methods used to control overall type I error, will be detailed in the SAP.

8.3.3. Exploratory Analyses

Additional efficacy and antiviral endpoints will be summarized descriptively. Any exploratory statistical analysis to be conducted on these endpoints will be documented in the SAP.

Resistance analyses, including assessment of treatment-emergent mutations in SARS-CoV-2 viral genes, will be documented in a separate resistance monitoring plan.

Exploratory sub-group analyses may also be conducted; these will be detailed in the SAP.

8.3.4. Safety Analyses

The treatment-emergent period for safety analyses is the time from first study drug administration to Day 29. All lab summaries will be presented by treatment group. Proportions of subjects experiencing treatment-emergent SAEs, AEs, and AEs resulting in treatment discontinuation will be summarized. Adverse event terms will be coded using MedDRA thesaurus terms. Treatment emergent events will be summarized by MedDRA SOC and preferred term, overall and by severity. For subjects experiencing an event with varying severity, the highest grade will be used in the summaries. Deaths and cause of death will be summarized.

Laboratory and vital sign data will also be summarized. Where applicable, laboratory abnormalities will be graded in accordance with the DAIDS severity scale. Shift tables for treatment emergent laboratory abnormalities will be presented.

Study treatment exposure (such as treatment duration and total dose received) will be summarized with descriptive statistics.

8.3.5. PK Analyses

Plasma concentrations of study drug and metabolites in sparse samples will be listed with time data and summarized using descriptive statistics, as applicable.

Additional details regarding safety and PK analyses will be provided in the SAP.

8.4. Interim Analyses

An independent DSMB will evaluate safety, efficacy, and futility, as described in the DSMB charter. Planned interim analyses will include:

- Futility analysis after 30% subjects in the supportive-care-only population are enrolled and have completed the follow-up period (Day 29)
- Interim efficacy, safety, futility analysis) after 65% in the supportive-care-only
 population are enrolled and have completed the follow-up period (Day 29)

Statistical testing will employ alpha spending and non-binding beta spending, both according to Lan-Demets approximation of O'Brien Fleming method. This controls the overall type I error rate at a one-sided 0.025 level. Total beta spending was specified at a 0.10 level. This corresponds to the following decision criteria

	Nominal p-values for decision			
Analysis	Futility (p > value)	Efficacy (p < value)		
Interim 1 ^a (30%)	0.8319			
Interim 2 (65%)	0.1738	0.0054		
Final	0.0233	0.0196		

No testing for efficacy will be carried out at Interim 1, but alpha-spending will be employed in accordance with the O'Brien-Fleming spending.

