4.3. Sample Size Considerations

The primary endpoint of proportion of subjects with all-cause hospitalization and all-cause mortality through Day 29 will be compared between treatments using a Cochran-Mantel-Haenszel (CMH) test adjusted for the stratification factors of age and region. The overall type I error will be controlled at a one-sided 0.025 level. Total beta spending was specified at a 0.10 level.

The study was planned to have interim analyses at 30% (futility only) and 65% (futility, safety and efficacy) of the originally planned number of subjects. The interim analyses were removed due to fast enrollment such that the final sample size was reached prior to the first planned interim analysis.

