4.3.1. Sample Size Justifications

Assuming the combined all-cause hospitalization and all-cause mortality rate will be 4% in the placebo arm, the sample size needed to detect a true 60% reduction (corresponding to an absolute difference in rates of 2.4%) in the BEM treatment arm with 90% power at a 1-sided significance

level of 2.5% was determined to be 1982 randomized participants in the supportive-care-only population. Sample size was calculated using SAS (version 9.4) for a 2-sample proportion Chisquare test. Considering the planned interim analyses with both alpha and beta spending according to Lan-Demets approximation of O'Brien Fleming method the sample size should be inflated by a multiplier of 1.055 to a target sample size of 2100 participants (see Section 11.1). Assuming 95% of randomized subjects who receive only supportive care as SOC will meet the mITT-S population criteria (see Section 6.5.4), the study targets total enrollment of 2210 subjects in the supportive-care-only population. If the true rate in the placebo arm is 3%, and assuming a reduction of 60% with BEM, the planned study has at least 80% power to detect a treatment effect. Planned enrollment in the combination arm is up to 300 subjects.

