5. PLANNED ANALYSES

5.1. Interim Analyses

A Data and Safety Monitoring Board (DSMB) will be responsible for ongoing monitoring of safety for the study. The DSMB members are independent of the study team and are external to the Sponsor. Unblinded analyses will be prepared and provided to the DSMB by an independent statistical group at the contract research organization (CRO). A DSMB charter describes the role of the DSMB in more detail.

Efficacy and futility interim analyses were planned at the beginning of this study but were removed due to fast enrollment such that the final sample size was reached prior to the first planned interim analysis.

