6.1. General Summary Table and Individual Subject Data Listing Considerations

Unless otherwise specified, continuous variables will be summarized by using the number of non-missing observations, arithmetic mean, standard deviation (SD), minimum, first quartile, median, third quartile and maximum values as summary statistics; categorical variables will be summarized by using the frequency count and the percentage of subjects in each category as summary statistics. Descriptive summaries will be tabulated by treatment group.

When a summary tabulates the number of subjects, subjects will only be counted once for a category (e.g., a particular adverse event type, a particular adverse event term, a particular concomitant medication) unless otherwise specified.

All statistical tests will be performed at a 0.025 significance level using one-sided tests, unless otherwise noted. Statistical tests will use stratification factors (age and region) according to randomization. Stratification factors may need to be removed or have their levels combined so that low or zero counts in one stratum do not invalidate relevant statistical tests.

Unless otherwise specified, all efficacy and virology analyses will be performed on the modified intent-to-treat (mITT) analysis populations for each stratum. All safety analyses, demographics, and baseline characteristics will be performed on the safety population. Refer to Section 6.5 for details on analysis population definitions.

All Safety, Efficacy, and Tolerability data will be listed. In cases where additional information may be helpful, considerations for listings will be noted in this document.

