11.2. Sample Size Calculation Details

The base sample size to have 90% power to detect a statistically significant reduction in the rate of hospitalization/death, given the study assumed rates of hospitalization, based on a one-sided 0.025 level test was computed using proc power is SAS (Version 9.4). This indicated that 991 subjects per arm (i.e. 1982 total subjects with 1:1 randomization). The corresponding code and output were:

```
proc power;
twosamplefreq test=pchi
power=0.9
groupproportions = (0.016, 0.04)
alpha=0.025
sides=1
npergroup=.
;
run;
```

The SAS System

The POWER Procedure Pearson Chi-square Test for Proportion Difference

Fixed Scenario Elements				
Distribution	Asymptotic normal			
Method	Normal approximation			
Number of Sides	1			
Alpha	0.025			
Group 1 Proportion	0.016			
Group 2 Proportion	0.04			
Nominal Power	0.9			
Null Proportion Difference	0			

Computed N per Group	
Actual Power	N per Group
0.900	991

The gsDesign function in the "gsDesign" package in R (Version 4.0.3) was used to identify the sample size adjustment and testing criteria needed to implement the planned interim analyses at 30% and 65% with O'Brien-Fleming spending for both alpha and beta (non-binding). The Lan-Demets spending function is used to approximate the O'Brien-Fleming boundaries (specified as sfLDOF in the code below). This indicated that a sample size inflation of 1.055 (at final) is needed for 90% power with overall type 1 error at one-sided 0.025 level. Total beta spending was specified at a 0.10 level. The corresponding code and output were:

```
Atea Pharmaceuticals, Inc.
                                                                                       Version 5
Statistical Analysis Plan - AT-03A-017
                                                                                   June 24, 2024
> gsDesign(k=3, test.type=4, alpha=0.025, beta=0.1, sfu=sfLDOF, sfl=sfLDOF, sflpar=-4, timing=c(0.3, 0.65,1))
Asymmetric two-sided group sequential design with
90 % power and 2.5 % Type I Error.
Upper bound spending computations assume
trial continues if lower bound is crossed.
          Sample
                  ----Lower bounds---- ----Upper bounds-----
          Size
 Analysis Ratio* Z Nominal p Spend+ Z Nominal p Spend++
        1 0.317 -0.96 0.1681 0.0027 3.93 0.0000 0.0000
        2 0.686 0.94 0.8262 0.0387 2.55 0.0054 0.0054
        3 1.055 1.99 0.9767 0.0587 1.99 0.0233 0.0196
                              0.1000
    Total

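### Protocol 8.4 prints the final alpha spend (0.0196) as the nominal efficacy p-value (correct: 0.0233), and the SAP never says its one-sided 0.025 test replaces it

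*Protocol*

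**What the plan says.** Protocol 8.4 plans two interim analyses, at 30% and 65% of the supportive-care-only population, with Lan-DeMets O'Brien-Fleming spending for alpha and non-binding beta. Of this scheme it says: "This controls the overall type I error rate at a one-sided 0.025 level". The table that follows, headed "Nominal p-values for decision", has a final row of futility p > 0.0233 and efficacy p < 0.0196.

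SAP 11.2 prints the gsDesign output for this design. The third-analysis row reads "3 1.055 1.99 0.9767 0.0587 1.99 0.0233 0.0196". Its last three entries are the upper-bound Z, the nominal p and the alpha spend.

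SAP 5.1 reports that the interim analyses "were removed due to fast enrollment such that the final sample size was reached prior to the first planned interim analysis". On the test level, SAP 4.3 says "The overall type I error will be controlled at a one-sided 0.025 level", and SAP 6.1 says "All statistical tests will be performed at a 0.025 significance level using one-sided tests, unless otherwise noted". SAP 8.3 repeats the 0.025 level for the primary hypothesis.

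SAP 2 names protocol version 2.0 as its basis. SAP 4.3.1 still derives the sample size by "Considering the planned interim analyses with both alpha and beta spending". No SAP sentence mentions the decision table in protocol 8.4.

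**The concern.** The final efficacy cell of the protocol table appears to come from the wrong column of the software output: the alpha increment stands where the nominal p-value belongs. The table itself gives a sign of this. In a design of this kind the final futility and efficacy bounds coincide, yet here a final p between 0.0196 and 0.0233 is neither efficacy nor futility.

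Removing the interims made the whole boundary set obsolete, but the SAP does not say so. A reader can find three candidate final thresholds: 0.0196 (protocol 8.4), 0.0233 (SAP 11.2) and 0.025 (SAP 4.3, 6.1 and 8.3). If the result fell between them, the primary verdict would depend on which document is read. So would the opening of the sequential secondary tests in SAP 8.5. Settling the matter after unblinding could look driven by the result.

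**Working it through.** **Inputs.** One-sided alpha 0.025, beta 0.10, looks at t = 0.30, 0.65 and 1 (protocol 8.4, SAP 11.2). Event rates 4% and 1.6%, 1:1 allocation (SAP 11.2). 2100 evaluable subjects, so 1050 per arm (SAP 4.3.1).

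**1. The plan's own design reproduces.** The chi-square sample size for 4% against 1.6% with 90% power at one-sided 0.025 is 991 per arm, 1982 in total, as stated. The group sequential inflation comes out at 1.0552 (stated: 1.055).

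**2. Alpha spending.** α(t) = 2[1 − Φ(2.2414/√t)], where 2.2414 is the normal quantile at 1 − 0.025/2.

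| t | Cumulative spend | Increment |
|---|---|---|
| 0.30 | 0.00004 | 0.00004 |
| 0.65 | 0.00543 | 0.00539 |
| 1.00 | 0.02500 | 0.01957 |

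The last increment is the 0.0196 in the protocol table.

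**3. Boundaries.** Solving for the upper bounds by recursive numerical integration, with futility ignored because it is non-binding, gives Z = 3.929, 2.548 and 1.990, that is nominal p = 0.00004, 0.0054 and 0.0233. The final value is also 0.0233 if no efficacy test is made at Interim 1.

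**4. Cell-by-cell comparison.** The protocol's futility column is one minus the lower-bound nominal p in SAP 11.2: 1 − 0.1681 = 0.8319, 1 − 0.8262 = 0.1738, 1 − 0.9767 = 0.0233. The Interim 2 efficacy cell, 0.0054, is correct; spend and nominal p round to the same figure there, which hides the mix-up. Only the final efficacy cell fails as a nominal p-value.

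**5. Effect in the planned three-look design.**

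| Final criterion | Overall type I error | Power at 4% placebo rate, futility honoured |
|---|---|---|
| 0.0233 | 0.0250 | 90.0% |
| 0.0196 | 0.0215 | 89.0% |

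**6. Effect in the single analysis now planned.** Power at 1050 per arm with a 60% reduction:

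| Level | Placebo rate 4% | Placebo rate 3% |
|---|---|---|
| 0.025 | 91.6% | 82.1% |
| 0.0233 | 91.1% | 81.3% |
| 0.0196 | 89.9% | 79.3% |

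**7. Chance of a disputed result.** Exact binomial enumeration with the one-sided pooled chi-square p, unstratified. The 50% and 40% reductions are assumptions, not figures from the plan.

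| Final p-value | Placebo rate | 60% reduction | 50% | 40% |
|---|---|---|---|---|
| 0.0196 to < 0.025 | 4% | 1.57% | 3.14% | 4.03% |
| 0.0196 to < 0.025 | 3% | 2.88% | 4.11% | 4.20% |
| 0.0233 to < 0.025 | 4% | 0.46% | 0.95% | 1.17% |
| 0.0233 to < 0.025 | 3% | 0.61% | 0.91% | 1.08% |

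A simulated CMH test over eight strata (assumed shares four of 15% and four of 10%; event rate equal across strata or doubled in the older half; 400,000 trials per setting) gives 1.63–3.15% at the design effect and 3.18–4.57% at 40–50% reductions for the wider zone.

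**8. Two examples, 1050 per arm.** z = (difference in proportions) / √[p̄(1 − p̄)(2/1050)], with p̄ the pooled rate.

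- 40 placebo and 24 BEM events: difference 16/1050 = 0.01524, p̄ = 64/2100 = 0.03048, z = 2.031, p = 0.0211. This fails 0.0196 and passes 0.0233 and 0.025.
- 42 and 26 events: same difference, p̄ = 68/2100 = 0.03238, z = 1.973, p = 0.0243. This fails 0.0196 and 0.0233 and passes 0.025.

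**The case against.** The best reply is that the SAP already settles the matter. The protocol table sits under the interim-analysis heading and belongs to a three-look design. The SAP says twice that those looks were dropped, sets one-sided 0.025 for all tests and again for the primary hypothesis, and prints the correct 0.0233 beside the spend. The protocol also defers detail to the SAP: "A statistical analysis plan (SAP) describing the detailed statistical methods will be developed and finalized before any analyses are performed". The spending text kept in SAP 4.3.1 explains how the sample size arose and does not keep the boundaries in force. A third-look boundary has no natural use in a one-look trial.

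Most of this stands. The operative level is 0.025, the printed error is on the safe side, and the probabilities in step 7 matter only if someone applies the protocol cell to the single final test. The larger ones also rest on assumed effects. But the reply does not make the printed figure correct, and it relies on an inference across two documents where one sentence would state the rule.

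**Conclusion.** The concern holds and is minor. The final efficacy cell in protocol 8.4 is wrong as a nominal p-value: it shows the spend, 0.0196, where the boundary is 0.0233. The sample size is unaffected, because it was computed with the correct boundary. Testing once at one-sided 0.025 is valid and does not inflate type I error, on the assumption that the DSMB's unblinded safety reviews included no efficacy stopping test; the charter is not among the documents. What remains is an unstated replacement of one threshold by another. It would affect the verdict with a probability of 1.6% to 2.9% at the design effect, and about 3% to 4.6% if the true reduction were 40–50%.

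**What to change.** Add one sentence to the SAP before unblinding: because no formal interim efficacy test was performed and no alpha was spent, the single final test at one-sided 0.025 replaces all decision criteria in protocol 8.4; the 0.0196 printed there was the alpha spend, and the nominal boundary of the planned design was 0.0233. Correcting the protocol cell to 0.0233 alone is not enough, since it would still differ from 0.025. Amending the protocol table is optional housekeeping.

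The cost is one sentence, with no further subjects, data or protocol amendment. The documents give the SAP version 5 date (June 24, 2024) but no unblinding date. If unblinding has already taken place, the clarification belongs in the clinical study report, with its timing stated.
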